6.3.2.3 Durable (or Sustained) Remission

This analysis is intended to compare the two treatment groups considering only the subjects that experienced remission (CDAI < 150 score) week 26 through week 52 (Sustained Remission). Subjects who are not in remission at any visit point assessment between 26 and 52 weeks will be considered as non-responders for this analysis. The same statistical method as used for the primary endpoint will be used for this analysis. The proportion (%) of subjects experienced sustained remission will be summarized for each treatment group and compared between the two treatments using Cochran-Mantel-Haenszel (CMH) chi-square test. Summary parameter estimates generated from the statistical analyses will be presented by treatment group, and will include the number and proportion of subjects achieving response along with the model estimated odds ratio (including 95% confidence interval) and p-value comparing RHB-104 treatment to placebo. The same sensitivity and exploratory analyses as for primary endpoint analysis will be conducted and summarized.

An additional complementary analysis and summary will be presented for the Proportion of subjects that maintained durable remission at least 3 out of the 4 visits assessed (i.e. $\geq 75\%$ of the visits in remission) week 26 through week 52.

6.3.2.4 Early Remission week 16

Early Remission week 16 will be derived following similar strategy as for the primary endpoint. The summary results will show the number and proportion (%) of subjects experienced early remission (CDAI < 150 score) week 16.

The same statistical approach as for the primary analysis will be employed to compare proportion (%) of subjects experienced Early Remission for the RHB-104 treated group versus Placebo treated group on ITT population using Cochran-Mantel-Haenszel (CMH) chi-square test controlling for the stratification variable anti-TNF agents use (yes/no). Summary parameter estimates generated from the statistical analyses will be presented by treatment group, and will include the number and proportion of subjects in remission along with the model estimated odds ratio (including 95% confidence interval) and p-value comparing RHB-104 treatment to placebo. The same sensitivity and exploratory analyses as for primary endpoint analysis may be conducted and summarized.

6.3.2.5 Steroid free remission week 52

This analysis is to compare the proportion (%) of subjects that achieved steroid free remission week 52 in the two treatment groups. To be considered to be in steroid free remission, a subject has to be in remission (CDAI score < 150) week 52 and is off steroids use for at least 3 weeks. The 3 weeks steroid free period is by week 49.

The statistical analysis strategy, the statistical tests comparing the two treatment groups, summary and presentation of the results will be similar to the primary endpoint analysis based on CMH chi-square tests. Summary parameter estimates generated from the statistical analyses will be presented by treatment group, and will include the number and proportion of subjects in steroid free remission along with the model estimated odds ratio (including 95% confidence interval) and p-value comparing RHB-104 treatment to placebo. The same sensitivity and exploratory analyses as for primary endpoint analysis may be conducted and summarized.

6.3.3 Supportive Secondary Efficacy Endpoints

This group of secondary efficacy endpoints is considered to be supportive of the efficacy for the primary and the key secondary endpoints. Therefore, there will be no multiplicity adjustments for this group of endpoints. Summary statistics and tests of hypotheses will be considered descriptive/supportive.

6.3.3.1 Time to Event Endpoints/Variables Analysis

The Time to event endpoints that will be analyzed includes:

- Time to remission
- Duration of remission
- Time to response
- Duration of response

The four endpoints will require time to event modeling approach. Cox Proportional Hazard modeling will be used to compare the time to event in both treatments while simultaneously adjusting for stratification variable anti-TNF agents use (yes/no). The explanatory variables in the model will include treatment, and the stratification variable anti-TNF agents use (yes/no). Patients who do not achieve the outcome event at the end of the study will be censored on the last visit date recorded. Patients who discontinued early will be censored on the last date of contact. Censored observations and confidence intervals for the estimated median times will be presented.

The null hypothesis that is tested is that of equal time to event distribution between the two treatments. Equality of the distributions of event times implies that there are similar response event rates between the two treatments not only for the entire treatment period, but also for any visit time point assessed post-baseline during the study. Rejection of the null hypothesis indicates that the event rates significantly differ between the two treatments at one or more visit time points assessed post-baseline. Kaplan Meier survival curves and parameters showing time-to-first observed response outcome will be summarized by treatment. Summary statistics that will be presented will include minimum, maximum, the 25th and 75th percentiles, 95% confidence intervals on the median (using the method of Brookmeyer and Crowley), and proportion of the events and censored data. The log-rank test will be used to test for differences between RHB-104 treatment and placebo, and p-values from the tests will be presented. Kaplan-Meier plots with descriptive summary statistics will be presented.

6.3.3.2 Sustained Remission week 16 through week 52

This analysis is intended to compare the two treatment groups based on the proportion (%) of subjects achieved Sustained Remission defined as maintaining CDAI score < 150 from week 16 through week 52. Subjects who are not in remission at any visit point assessment between week 16 and week 52 will be considered as non-responders for this analysis. The same statistical method as used for the primary endpoint will be used for this analysis. The proportion (%) of subjects experienced sustained remission will be summarized for each treatment group and compared between the two treatments using Cochran-Mantel-Haenszel (CMH) chi-square test. Summary parameter estimates generated from the statistical analyses will be presented by treatment group, and will include the number and proportion of subjects achieving sustained remission along with the model estimated odds ratio (including 95% confidence interval) and p-value comparing RHB-104 treatment to placebo.

An additional complementary analysis and summary will be presented for the Proportion of subjects that maintained durable remission at least 5 out of the 6 visits assessed (i.e. $\geq 83\%$ of the visits in remission) week 16 through week 52.

6.3.3.3 Response at Week 52

The Response is defined as reduction from baseline of ≥ 100 in CDAI score week 52. The responders will include subjects who were responders week 26 through week 52 and the subjects that were non-responders at week 26 but were responders week 52 (Late Responders).

The same statistical methods as used for the primary endpoint will be used for this analysis. The proportion of subjects experienced response at 52 weeks will be summarized for each treatment

group and compared between the two treatment groups using Cochran-Mantel-Haenszel (CMH) chi-square test.

6.3.3.4 Early Response week 16

The Early Response week 16 is defined as the proportion (%) of subjects that experienced reduction from baseline of ≥ 100 in CDAI score. The same statistical methods as used for the primary endpoint will be used for this analysis. The proportion of subjects (%) experienced early response week 16 will be summarized for each treatment group and compared between the two treatments using Cochran-Mantel-Haenszel (CMH) chi-square test. Summary parameter estimates generated from the statistical analyses will be presented by treatment group, and will include the number and proportion of subjects achieving response along with the model estimated odds ratio (including 95% confidence interval) and p-value comparing RHB-104 treatment to placebo.

6.3.3.5 Steroid free remission week 26

This analysis is to compare the proportion (%) of subjects that achieved steroid free remission week 26 comparing the two treatment groups. To be considered to be in steroid free remission subject has to be in remission (CDAI score < 150) week 26 and maintained off steroids for at least 3 weeks. The 3 weeks steroid free period is by week 23.

The statistical analysis strategy, the statistical tests comparing the two treatment groups, summary and presentation of the results will be similar to the primary endpoint analysis based on CMH chi-square tests. Summary parameter estimates generated from the statistical analyses will be presented by treatment group, and will include the number and proportion of subjects achieving response along with the model estimated odds ratio (including 95% confidence interval) and p-value comparing RHB-104 treatment to placebo.

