3. STUDY DESIGN

This study is a multicenter, Phase III, randomized, placebo-controlled, parallel group, double-blind study designed to evaluate the efficacy and safety of RHB-104 compared to placebo to treat subjects with moderate to severe CD. RHB-104 consists of 3 antibiotics with activity against *Mycobacterium avium subsp. paratuberculosis* (MAP), a potential cause of CD. Subjects with active CD will be randomized at baseline in a 1:1 fashion to receive up to 52 weeks of RHB-104 or placebo. Subjects will remain on stable doses of their baseline CD treatment although steroids may be tapered after Week 8 at the discretion of the investigator.

The study is designed to assess remission at Week 26 as the primary endpoint. However, as MAP are slow growing mycobacteria without a proven antibiotic treatment, the duration of antibiotic treatment needed to achieve remission in subjects with CD caused by MAP may be longer than 26 weeks. Subjects with response at week 26 may ultimately achieve remission at a later time point with continued treatment for MAP. Also, subjects with CD treated for underlying MAP infection may experience benefits with a longer period of time in response or remission with RHB-104 treatment compared to placebo. Thus, the study is also designed to assess response, remission, and maintenance of remission in subjects on randomized treatment through week 52.

Blood samples will be collected at baseline and at every visit after the initial 4 weeks of treatment to test for MAP in the serum using a polymerase chain reaction (PCR) assay. MAP cultures will be prepared from whole blood at the baseline visit and after 26 and 52 weeks of treatment in subjects enrolled at North American study sites.

Safety and pharmacokinetics of the fixed-dose combination product, RHB-104, will also be assessed. Colonoscopy will be done in consenting subjects prior to initiation of study drug and after 26 weeks of study drug to assess for mucosal healing as well as MAP status via PCR and culture. Optional biopsies will also be collected for possible measurement of tissue drug levels and archived for future MAP determinations.

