4.3 Randomization and Treatment Assignment Procedures

A total of 410 subjects that meet study eligibility requirements will be randomly assigned in permuted blocks to receive active (RHB-104) or placebo treatment in a 1:1 ratio using an Interactive Web Randomization System (IWRS). Randomization will be performed within strata defined by whether subjects use protocol permitted anti-TNF agents (yes/no). The randomization

code will only be available to personnel responsible for the randomization of subjects or labeling of the study drug. The sponsor and all personnel involved in the conduct of the study will be blinded to the treatment assigned to each subject.

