6.3.1 Primary Efficacy Analysis

The primary efficacy analysis will be performed on ITT population. Sensitivity analyses may be performed on Observed Case (completers only), on subjects with no violation of key inclusion/exclusion criteria (mITT population), and on PP population.

The primary efficacy variable is the proportion of subjects experienced remission week 26, where remission is defined as a subject having a Crohn's Disease Activity Index (CDAI) score of < 150 . Subjects who have a week 26 CDAI measurement ≥ 150 or who do not have a CDAI measurement week 26 will be classified as not achieved remission. The primary analysis will compare the RHB-104 treated group to Placebo treated group on ITT population using Cochran-Mantel-Haenszel (CMH) chi-square test controlling for the stratification variable anti-TNF agents use (yes/no). The null and alternative hypotheses are as follows, where π_R and π_P are the proportion of subjects with remission in the RHB-104 and placebo treated groups, respectively.

Null hypothesis $H_0: \pi_R = \pi_P$

"Proportion (%) of subjects in Remission in RHB-104 Treatment is equal to Proportion (%) of subjects in Remission in Placebo Treatment at week 26"

Alternative hypothesis $H_1: \pi_R \neq \pi_P$

"Proportion of subjects in Remission for RHB-104 Treatment is not equal to Proportion of subjects in Remission for Placebo treatment at week 26"

For each treatment group, descriptive statistics will be presented including the number of observations, proportion (%) of subjects in remission.

The primary analysis will compare RHB-104 group to the placebo group using a two-sided test at the $\alpha = 0.049$ level of significance.

The statistical criterion for primary objective success will be met if the CMH chi-square test p-value comparing the RHB-104 arm with the placebo arm (Higher proportion in RHB-104 than placebo) is less than 0.049 based on a 2-sided test taking into account the pre-specified protocol alpha spent at interim equal to 0.003.

For each treatment group, parameter estimates with 95% confidence interval will be presented including the number of observations and proportion (%) of subjects in remission.

To assess the robustness of the primary results, sensitivity analysis will be performed on mITT and on observed case (only completers with 26 weeks of data). The observed case population will include only subjects that have 26 weeks assessment.

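### The log-rank test for the time-to-event endpoints is specified without the randomisation stratum that the Cox model adjusts for, and the SAP does not say which p-value is the main one

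*SAP*

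**What the plan says.** SAP 4.3 sets the design: "Randomization will be performed within strata defined by whether subjects use protocol permitted anti-TNF agents (yes/no"). Allocation is 1:1 (SAP 3).

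SAP 6.3.3.1 covers four endpoints: time to remission, duration of remission, time to response and duration of response. It gives two treatment comparisons for each.

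- A Cox model is used "to compare the time to event in both treatments while simultaneously adjusting for stratification variable anti-TNF agents use". The next sentence repeats the factor: "The explanatory variables in the model will include treatment, and the stratification variable anti-TNF agents use (yes/no").
- A log-rank test accompanies the Kaplan-Meier summaries: "The log-rank test will be used to test for differences between RHB-104 treatment and placebo, and p-values from the tests will be presented". It names no stratum and does not refer back to a stratified method.

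The primary analysis in SAP 6.3.1 does name the factor, as a Cochran-Mantel-Haenszel (CMH) "chi-square test controlling for the stratification variable anti-TNF agents use (yes/no"). On the standing of the time-to-event family, SAP 6.3.3 says: "Summary statistics and tests of hypotheses will be considered descriptive/supportive". SAP 6.1.2 leaves p-values outside the hierarchy unadjusted and nominal.

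**The concern.** When randomisation is stratified on a prognostic factor, an analysis that ignores the factor leaves between-stratum variation in the comparison although the design has balanced it out. It also estimates a pooled effect that is somewhat diluted relative to the effect within strata. For a log-rank test the expected result is mild conservatism and some loss of power.

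The second issue is practical. Each endpoint will carry two p-values, one adjusted for the stratum and one, as written, not. The SAP does not rank them. If they disagree, the choice of which to emphasise would be made after unblinding.

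**Working it through.** **1. What the text leads a programmer to do.** The stratum is named in the primary CMH test (6.3.1), the logistic model (6.3.1), the ANCOVA models (6.3.3.6 to 6.3.3.10) and the Cox model (6.3.3.1). Some CMH sentences omit it (6.3.2.2, 6.3.2.3, 6.3.3.2 to 6.3.3.4), but those sections say that the primary-endpoint method applies, which brings it in. The log-rank sentence has neither the factor nor such a link. Followed literally, it gives an ordinary log-rank test.

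**2. The plan's own figure.** The documents give no power or event count for the time-to-event endpoints. The only design figure to check is the primary one (SAP 6.1.9): 36% v 21%, two-sided 0.05, 90% power.

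n per arm = [z(α/2)·√(2p̄q̄) + z(β)·√(p₁q₁ + p₂q₂)]² / δ², with p̄ = 0.285 and δ = 0.15

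= [1.960·√0.40755 + 1.282·√0.3963]² / 0.0225 = 189 (190 at α = 0.049). With continuity correction it is 202 (203 at 0.049), within 2 or 3 of the stated 205. At 162 per arm, power is 85.2% (85.0% at 0.049), consistent with the stated minimum of 80%.

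**3. Effect on the hazard scale.** With exponential times, λ = −ln(1 − p)/26.

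- 36% v 21%: HR = ln(0.64)/ln(0.79) = 1.89.
- 30% v 21% (the 9-point clinically meaningful difference in SAP 6.1.9): HR = ln(0.70)/ln(0.79) = 1.51.

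**4. Tests compared.** At each visit k, U = Σ(d₁ₖ − dₖn₁ₖ/nₖ), with hypergeometric variance V. The unstratified statistic is Z = U/√V from the pooled data. The stratified statistic is Z = (U_A + U_B)/√(V_A + V_B), computed within the two anti-TNF strata and then summed. The Cox model has treatment and stratum as covariates (Efron ties, Wald test).

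**5. Simulation for time to remission.** From the documents: 324 patients, 1:1 within strata, CDAI at weeks 4, 8, 12, 16, 20, 26, 35, 44 and 52, and the week-26 remission rates. Assumed: exponential times, 20% dropout by week 52, 20% to 50% on anti-TNF agents, and a remission hazard in that stratum of 0.33 to 1 times that of the other. Tests are two-sided at 0.05. There were 4,000 trials per setting at 36% v 21%, 6,000 at 30% v 21% and 10,000 under the null. Selected settings:

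| Week-26 remission | On anti-TNF | Stratum HR | Unstratified log-rank rejects | Stratified log-rank rejects | Unstratified log-rank and Cox disagree |
|---|---|---|---|---|---|
| 36% v 21% | 35% | 1 | 96.1% | 96.1% | 0.2% |
| 36% v 21% | 35% | 0.5 | 96.3% | 96.6% | 0.9% |
| 36% v 21% | 50% | 0.33 | 95.6% | 97.4% | 1.8% |
| 30% v 21% | 35% | 1 | 63.9% | 63.9% | 1.1% |
| 30% v 21% | 35% | 0.5 | 63.4% | 65.0% | 3.2% |
| 30% v 21% | 50% | 0.33 | 62.1% | 67.0% | 5.9% |
| No effect | 35% | 1 | 5.2% | 5.3% | 0.3% |
| No effect | 35% | 0.5 | 4.3% | 4.6% | 0.7% |
| No effect | 50% | 0.33 | 4.2% | 5.2% | 1.5% |

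The loss from not stratifying is therefore 0, 0.3 and 1.8 points at 36% v 21%, and 0, 1.6 and 4.9 points at 30% v 21%. Under the null, the Monte Carlo standard error is √(0.05·0.95/10,000) = 0.2 points, so the rejection rates of 4.2% and 4.3% do reflect conservatism.

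A second simulation on the same visit grid, with a prognostic stratum, put the gain from stratifying at about 0.6 to 1.4 points (36% v 21%) and 1.4 to 6.6 points (30% v 21%). A third, at HR 1.5 with 30% to 50% on anti-TNF agents and a stratum HR of 0.3 to 0.5, raised power from 69.7% to 71.2%, 62.0% to 66.0% and 60.1% to 63.9%. The ranges quoted in the conclusion cover all three.

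**The case against.** - **The SAP never calls the test unstratified.** This is right: the reading comes from silence, and the SAP omits the stratum elsewhere too. But the other omissions are covered by a reference to the primary method, and this one is not. The exact statement is that stratification is not specified, and that the literal reading gives an ordinary test.
- **A reader might infer that the log-rank p-value will be the weaker one.** The documents do not support that. They give no prognostic effect of anti-TNF use and no prevalence. With a non-prognostic stratum the two log-rank tests had the same power, and under the alternatives only the unstratified test was significant in 0.1% to 0.8% of trials.
- **Disagreement with Cox is not all due to stratification.** This stands. With a non-prognostic stratum, 0.2% to 1.1% of trials still disagreed in the settings tabulated with a treatment effect.
- **A stratum-adjusted comparison already exists, and a plain log-rank test suits unstratified Kaplan-Meier curves.** This is fair and limits the harm. It does not settle which p-value is the main one.
- **Nothing is decided on these p-values.** This is also right. It makes the point minor but does not remove the inconsistency.

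**Conclusion.** The point holds as a minor specification gap. As written, the log-rank p-value ignores the stratum used in randomisation and in the Cox model, and the SAP does not say which of the two p-values is the main one.

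If anti-TNF use is prognostic, the unstratified test loses on average about 0 to 2 power points at the design effect (36% v 21%) and about 0 to 7 at 30% v 21%. If it is not prognostic, nothing is lost. The unstratified log-rank and the adjusted Cox results fell on opposite sides of 0.05 in 0.2% to 1.8% of trials at the design effect, and in 1.1% to 5.9% at the smaller one.

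It would be wrong to infer inflated type I error: the unstratified test rejected in 4.2% to 5.2% of null trials. Nor is any labelling claim at risk, because these endpoints are descriptive and lie outside the testing hierarchy.

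The sizes rest on assumed prevalence, stratum effect, dropout and exponential times, and were checked only for time to remission. Duration of remission and of response are computed only in patients who achieve the outcome (SAP 2.2.3.2). Randomisation does not guarantee stratum balance in that subset, so the figures do not carry over to those two endpoints.

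**What to change.** In SAP 6.3.3.1, specify a log-rank test stratified by randomised anti-TNF use (yes/no) for all four endpoints. For each endpoint, also state in advance whether the Cox or the stratified log-rank p-value is the main one. The second change is needed as well, because stratifying the log-rank test still leaves two p-values per endpoint.

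The cost is one phrase, one added sentence and one program option. In the non-prognostic settings tried, stratifying cost no power. SAP 6.8 provides for changes made before the database is unblinded.

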6.3.3.6 Quality of Life Assessment: SF-36 Questionnaire Total Score

The SF-36 Health Survey is a self-administered, 36-item questionnaire designed to measure 8 domains of functional health status and well-being. For this study, the questionnaire data is collected at baseline, week 26 and week 52. The SF-36 instrument guidelines will be used to assess and summarize the overall health status. The SF-36 consists of 8 scaled scores with range 0-100 with higher score indicating better health. The 8 sections or domains are:

- Vitality
- Physical functioning
- Bodily Pain
- General Health Perceptions
- Physical Role Functioning
- Emotional Role Functioning
- Social Role Functioning
- Mental Health

There are also two component scores. The Physical Component Summary Score is a composite of the Physical Functioning, Role Functioning, Bodily Pain and General Health scales. The Mental Health Component Summary Score is a composite of the Vitality, Social Functioning, Role-Emotional and Mental Health scales.

All above-mentioned domain and component scores will be provided by QualityMetric to inVentiv for data summary and analysis.

Summary descriptive statistics including mean, standard deviation, median and range (including 95% confidence intervals) will be presented in tables and bar graphs for the actual and change from baseline scores for each domain and component summary score by treatment and by visit. The change from baseline for each domain and component summary score will be analyzed using an analysis of covariance (ANCOVA) model with treatment group, stratification variable anti-TNF agents use (yes/no) as classification factors, and baseline score as covariate. The treatment parameter estimates from the analysis models including means, 95% confidence intervals and associated 2-sided p-values will be presented.

